Good Laboratory Practice (GLP)-complaint toxicity studies of up to 14 days duration have been conducted with RV299 in rats (25, 80, 250 mg/kg/day) and dogs (15, 50, 150 mg/kg/day), by once daily oral administration. The highest dose tested in rats, 250 mg/kg/day, was considered the no-observed-adverse-effect-level (NOAEL). In dogs, adverse clinical observations were noted at 150 mg/kg/day and animals assigned to a 2-week recovery period were terminated prematurely within 5 days of cessation of dosing. The principal target organs for toxicity were lymphohematopoietic tissues. Marked myelosuppression/immunodepression, including thrombocytopenia, decreases in reticulocyte and white cell counts and pronounced decreases in cellularity in bone marrow and lymphoid tissues, were noted at 50 mg/kg/day and 150 mg/kg/day. Adverse effects (inflammation and atrophy) were also noted in the gall bladder. These findings were noted where mean maximum observed plasma concentration (C_{\max}) and area under the plasma concentration-time curve over the last 24 hours dosing interval (AUC_{0-24h}) values were 4-fold greater than the mean values following a clinical dose of 65 mg twice a day (bis in die; BID).

Overall, data from *in vitro* and *in vivo* for genotoxicity studies demonstrated RV299 was not genotoxic.

RV299 had no effects on the respiratory, or central nervous systems in rats at oral doses up to 250 mg/kg, nor on the cardiovascular system of telemetered dogs at an oral dose of 50 mg/kg.

RV299 has been evaluated in a single clinical study (REVD001) in a total of 32 healthy adult subjects and a cumulative total of 136 doses spanning single doses of 25 to 125 mg and multiple doses of 35 to 65 mg BID for 9 doses. The study also included 10 subjects on matched placebo. The study is ongoing and so the data from this study is still blinded and the safety profile of RV299 has therefore been assessed in aggregate form with placebo.

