Oral dosing with RV299	
 1) RV299 has not previously been tested in human subjects infected with RSV and may not confer any antiviral protection against RSV in humans despite encouraging pre-clinical evidence. 2) Pre-clinical studies have identified myelosuppressive effects (including reduced reticulocytes, platelets and white cell counts and fractions) in dogs following 14 days' administration at doses well in excess of the intended human dose (50mg/kg/day). No such effects were seen at 15mg/kg/day and this dose was used to set the NOAEL for human administration of RV299. 3) RV299 has shown variable PK with some subjects experiencing higher exposures (doubling) for a given dose than other subjects, possibly due to differences in clearance. 	
 1) Subjects will be monitored for severe RSV-related disease throughout the study and managed accordingly with supportive measures and may be withdrawn from the study at the investigator's discretion at any time. 2) The 65mg dose has been administrated to healthy human volunteers twice daily for 5 days and there has been no evidence of myelosuppressive effects during dosing or during the 3-week follow-up period after the last dose. The same study confirmed that the 65mg dose produces PK exposures in humans that are 2- to 4-fold below the NOAEL, providing an adequate safety margin. Subjects in the viral challenge study will have safety bloods assessed throughout the dosing interval and during follow-up to continue to monitor for any myelosuppressive effects. 3) The dose has been selected to ensure that the NOAEL safety margin is not exceeded even in subjects who may experience doubling in RV299 exposure for a given dose.
Oral dosing with placebo	Given that the placebo is a pharmacologically inert material, there should be no risk.	Not applicable.

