Following challenge agent inoculation all unexpected (in the opinion of the PI/investigator) pyrexia will be captured as an AE, along with all other occurrences that meet the criteria for an AE.

Spirometry

A 15% drop in a spirometry value (compared to baseline) confirmed by a repeat on the same day, will be a Grade 1 (mild) AE. The PI/investigator will use his/her clinical judgement to assign severity grades above Grade 1, based on evaluation of clinical signs and symptoms. If the repeated value has returned to normal an AE will not be raised.

Laboratory Values

Deterioration in a laboratory value (compared to baseline) should only be reported as an AE if the deterioration meets the criteria for an AE and is deemed to be clinically significant (in the opinion of the PI/investigator). If deterioration in a laboratory result is associated with clinical signs and symptoms, the sign or symptom will be reported as an AE and the associated laboratory result will be considered as additional information.

The PI/investigator and/or SME will judge whether abnormal laboratory values are clinically significant or not clinically significant, and record this in the source document. This entry should be signed and dated by the relevant PI/investigator. Laboratory abnormalities detected at screening will be considered as part of the medical history and will not be reported as AEs.

Challenge agent associated laboratory abnormalities (e.g., elevated alanine transferase, aspartate aminotransferase, or gamma glutamyl transferase; decreased neutrophils) may be recorded as AEs (at the discretion of the PI/investigator).

C-reactive Protein

Any value above 5 mg/L but less than 60 mg/L will be a Grade 1 (mild) AE (unless deemed non clinically significant by the PI/investigator). The PI/investigator will use his/her clinical judgement to assign severity grades above Grade 1, based on evaluation of clinical signs and symptoms.

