10.9.2. Laboratory Variables

For all laboratory variables, baseline is defined as the assessment collected prior to the first administration of IMP.

The following parameters will be included within summary presentations (and presented in the units as shown):

- Haematology: platelet count ($10^9/L$), white blood cell (WBC) count (absolute) ($10^9/L$), neutrophils (% and absolute ($10^9/L$)), lymphocytes (% and absolute ($10^9/L$)), monocytes (% and absolute ($10^9/L$)), eosinophils (% and absolute ($10^9/L$)), basophils (% and absolute ($10^9/L$)), red blood cell (RBC) count ($10^{12}/L$), reticulocyte count (% and absolute ($10^9/L$)), haemoglobin (g/L), haematocrit (%), mean corpuscular volume (MCV) (fL), mean corpuscular haemoglobin (MCH) (PG), mean corpuscular haemoglobin concentration (MCHC) (g/L).
- Coagulation: prothrombin time (PT) (secs), activated partial thromboplastin time (APTT) (secs).
- Biochemistry: sodium (mmol/L), potassium (mmol/L), glucose (mmol/L), albumin (g/L), chloride (mmol/L), bicarbonate (mmol/L), calcium (mmol/L), uric acid (umol/L), total protein (g/L), creatinine (umol/L), total bilirubin (umol/L), indirect bilirubin (umol/L), direct bilirubin (umol/L), inorganic phosphate (mmol/L), blood urea nitrogen (mg/dL), C-reactive protein (CRP) (mg/L), gamma glutamyl transferase (GGT) (IU/L), alkaline phosphatase (ALP) (IU/L), alanine transaminase (ALT) (IU/L), lactate dehydrogenase (LDH) (IU/L), aspartate transaminase (AST) (IU/L), urea (mmol/L).
- Thyroid Function Tests (screening only): Free thyroxine (pmol/L), Thyroid Stimulating Hormone (mIU/L).
- Cardiac Enzymes: creatine kinase (IU/L), troponin T (ng/L).
- Urinalysis: colour, specific gravity, appearance, pH, dipstick presence of: blood, glucose, leukocytes, ketones, nitrite, protein, urobilinogen, bilirubin.

- Human Immunodeficiency Virus and Hepatitis A, B and C: HIV-1 and HIV-2 antibodies, hepatitis A antibodies (HepA IgM), hepatitis B surface antigen (HBsAg), hepatitis C antibodies (HCAb).

Observed parameter values and changes from baseline will be summarised appropriately for the above haematology, chemistry, coagulation and cardiac enzyme parameters. Any other laboratory parameters collected as part of the study will only be included in participant listings. Laboratory data collected in different units to that shown will be converted to the above specified units (if possible) for presentation in tables and listings.

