Laboratory values outside the reference range will be identified in the participant listings as above or below the reference range. Laboratory values that are below the limit of quantification (BLQ) will be set to zero in computations for summary presentations but will be noted as BLQ in participant listings. Laboratory values that are missing will remain missing and will be noted as such in listings.

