14.2.3.7	Time to Symptom Resolution by 10-Item Diary Card from Initial Administration of IMP to 24-Hours Symptom Free - ITT-I Population	X			
14.2.3.8	Time to Symptom Resolution by 10-Item Diary Card from Peak Total Symptom Score to 24-Hours Symptom Free - ITT-I Population	X			

Table Number	Table Title	Repeated for ITT- A ITT- B ITT PP
14.2.3.9	Time to Peak Symptom Score by 10-Item Diary Card from Initial Administration of IMP - ITT-I Population	X
14.2.4.1	Total Weight of Mucus Produced from Initial Administration of IMP to Quarantine Discharge by Assessment - ITT-I Population	X
14.2.4.2	Total Number of Tissues Used from Initial Administration of IMP to Quarantine Discharge by Assessment - ITT-I Population	
CCI	[REDACTED]	
	[REDACTED]	
14.3.1.1	Overall Summary of Treatment Emergent Adverse Events – Safety Population	
14.3.1.2	Treatment Emergent Adverse Events by System Organ Class and Preferred Term – Safety Population	
14.3.1.3	Treatment Emergent Adverse Events by System Organ Class, Preferred Term and Severity – Safety Population	
14.3.1.4	Treatment Emergent Adverse Events Related to RV299 by System Organ Class and Preferred Term – Safety Population	
14.3.1.5	Adverse Events Related to Challenge Agent by System Organ Class and Preferred Term – Safety Population	
14.3.2	Haematology Parameters: Summary – Safety Population	
14.3.3	Biochemistry Parameters: Summary – Safety Population	
14.3.4	Coagulation Parameters: Summary – Safety Population	
14.3.5	Cardiac Enzymes Parameters: Summary – Safety Population	
14.3.6	Urinalysis Parameters: Summary – Safety Population	
14.3.7	Vital Signs Parameters: Summary – Safety Population	
14.3.8	Spirometry Parameters: Summary – Safety Population	
14.3.9	12-Lead Electrocardiogram Parameters: Summary – Safety Population	

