
Parameter (units)	Treatment Group		Placebo	
	RV299 (N=xx)	Observed Change from Baseline	Observed	Placebo (N=xx)
Baseline				
n	XX		XX	
Mean (SD)	XX.X (XX.XX)		XX.X (XX.XX)	
%CV	XX.XX		XX.XX	
Median	XX.X		XX.X	
Q1, Q3	XX.X, X.XX		XX.X, X.XX	
Min, Max	XX, XX		XX, XX	
Day 7				
n	XX	XX	XX	XX
Mean (SD)	XX.X (XX.XX)	XX.X (XX.XX)	XX.X (XX.XX)	XX.X (XX.XX)
%CV	XX.XX	XX.XX	XX.XX	XX.XX
Median	XX.X	XX.X	XX.X	XX.X
Q1, Q3	XX.X, X.XX	XX.X, X.XX	XX.X, X.XX	XX.X, X.XX
Min, Max	XX, XX	XX, XX	XX, XX	XX, XX
[Repeat for all scheduled post-baseline assessments and parameters]				

This layout will be utilised for the following tables:

Table 14.3.3	Biochemistry Parameters: Summary - Safety Population
Table 14.3.4	Coagulation Parameters: Summary - Safety Population
Table 14.3.5	Cardiac Enzyme Parameters: Summary - Safety Population
Table 14.3.6	Urinalysis Parameters: Summary - Safety Population
Table 14.3.7	Vital Signs Parameters: Summary - Safety Population
Table 14.3.8	Spirometry Parameters: Summary - Safety Population
Table 14.3.9	12-Lead Electrocardiogram Parameters: Summary - Safety Population

Listing 16.2.1.1
Participant Disposition

Treatment Group	Participant Number / Randomisation Number	Date/Time of Informed Consent:	Date/Time of:	Eligible for randomisation? [1] / Completed IMP? / Completed Study? [2]	Reason not randomized / Reason for discontinuation of IMP / Reason for withdrawal
		V2 / V3 / V5.1 / V8 / Genetic testing V1 / Genetic testing V2	Quarantine Admission / Randomisation / Challenge Agent Administration / First IMP Administration / Quarantine Discharge		
xxxxxx	xxxxxx / xxxxxx	ddmmmyyyy hh:mm / NA / ddmmmyyyy hh:mm / ddmmmyyyy hh:mm / NA / ddmmmyyyy hh:mm	ddmmmyyyy hh:mm / ddmmmyyyy hh:mm / ddmmmyyyy hh:mm / ddmmmyyyy hh:mm / ddmmmyyyy hh:mm	Yes or No / Yes or No / Yes or No	xxxxxxxxxxxxxxxxxx / xxxxxxxxxxxxxxxxxx / xxxxxxxxxxxxxxxxxx

NA = Not applicable.

[1] Eligible for randomisation based on criteria at Admission (Day -2/-1).

[2] Completed Study = Participating in the study up to and including Day 28 (Follow-up).

Listing 16.2.1.2
Failed Inclusion and Exclusion Criteria

Treatment Group	Participant	Reason for Exclusion
xxxxxxx	xxxxxx	xxxxxxxxxxxxxxxxxxxx

Programming note: Listing not required if no participants fail the criteria.

Listing 16.2.74
Protocol Deviations

Treatment Group	Participant	Deviations Reported	Date Occurred (Study Day)	Deviation Category [a]	Other, Specify	Deviation Description	Serious Breach?

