				WBC Count	x.xx	x.xx	$\times 10^9/L$	x.x	xx.x		

L = below lower limit, H = above upper limit.

This layout will be utilised for the following listings:

- Listing 16.2.8.3 Coagulation
- Listing 16.2.8.4 Biochemistry
- Listing 16.2.8.5 Cardiac Enzymes
- Listing 16.2.8.6 Thyroid Function Tests

Listing 16.2.8.100
 Other Laboratory Tests: TDL

Treatment Group	Participant	Visit	Sample Collection Date / Time (Study Day)	Test	Result
xxxxxxx	xxxxxx	xxxx	ddmmmyyyy / hh:mm (xx)	HIV 1 and HIV 2 antibodies Hepatitis A Hepatitis B Hepatitis C FSH Beta HCG (IU/L) Immunoglobulin A antibodies HbA1C (%) HbA1C (mmol/mol)	Positive / Negative Positive / Negative Positive / Negative Positive / Negative xx.x Positive / Negative xx.x xx.x xx.x

L = Low, H = High, ND = Not Done.

Programming Note: Normal Ranges to be displayed in footnote, if available.

Listing 16.2.8.101
Other Laboratory Tests: Urine Pregnancy

Treatment Group	Participant	Visit	Test Date / Time (Study Day)	Participant has data	Result	Comments
xxxxxx	xxxxxx	xxxx	ddmmYYYY / hh:mm (xx)	Yes / No / NA - Male	Positive / Negative	xxxxxxxxxxxxxxxxxxxx

Listing 16.2.8.9.2
Other Laboratory Tests: Drugs of Abuse Screen

Treatment Group	Participant	Visit	Sample Collection Date / Time (Study Day)	Test Performed Time	Drug	Result	Comments
xxxxxx	xxxxxx	xxxx	ddmmmyyyy hh:mm (xx)	hh:mm	Cocaine	Positive / Negative / Not done	
					Cannabinoids	Positive / Negative / Not done	
					Methadone	Positive / Negative / Not done	
					Ecstasy	Positive / Negative / Not done	
					Opiates	Positive / Negative / Not done	
					Benzodiazepines	Positive / Negative / Not done	
					Barbituates	Positive / Negative / Not done	
					Amphetamine	Positive / Negative / Not done	
					Methamphetamine	Positive / Negative / Not done	
					Tricyclic	Positive / Negative / Not done	

Listing 16.2.8.9.
Other Laboratory Tests: Urine Cotinine

Treatment Group	Participant	Visit	Test Performed Date / Time (Study Day)	Result	Comments
xxxxxx	xxxxxx	xxxx	ddmmYYYY / hh:mm (xx)	Positive / Negative	xxxxxxxxxxxxxxxxxx

Listing 16.2.8.9.
Other Laboratory Tests: Alcohol Breath Test

Treatment Group	Participant	Visit	Test Date / Time (Study Day)	Result	Comments
xxxxxx	xxxxxx	xxxx	ddmmyyyy / hh:mm (xx)	Positive / Negative	xxxxxxxxxxxxxxxxxx

Listing 16.2.9.
Urinalysis

Treatment Group	Participant	Visit	Sample Collection Date / Time (Study Day)	Test Performed Time	Parameter	Result [1]

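### Myelosuppression is a named RV299 risk, but the planned safety tables count low blood counts by arm only when they are reported as adverse events; no table counts new measured lows after first dose

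*SAP*

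**What the plan says.** **The risk.** Protocol 2.2.1 reports from the dog toxicity studies "Marked myelosuppression/immunodepression, including thrombocytopenia, decreases in reticulocyte and white cell counts". Table 2-1 in Protocol 2.5.1 carries this forward as a risk of oral RV299. Part of the stated mitigation is that participants "will have safety bloods assessed throughout the dosing interval and during follow-up to continue to monitor for any myelosuppressive effects".

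**The laboratory tables.** SAP 10.9.2 states: "Observed parameter values and changes from baseline will be summarised appropriately for the above haematology, chemistry, coagulation and cardiac enzyme parameters". SAP 13.2 lists one haematology table, 14.3.2 ("Haematology Parameters: Summary – Safety Population"). Its shell in SAP 14 gives n, mean (SD), %CV, median, quartiles, minimum and maximum, for observed values and change from baseline, by arm and visit, with the instruction "Repeat for all scheduled post-baseline assessments and parameters". The safety tables run from 14.3.1.1 to 14.3.9 without a numbering gap. None is a count, shift or grade table for laboratory values, and the redacted rows in that list come before 14.3.1.1.

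**The flags.** SAP 10.9.2 says "Laboratory values outside the reference range will be identified in the participant listings as above or below the reference range". The haematology listing shell holds the result, change, limits and a flag, footnoted "L = below lower limit, H = above upper limit". It has no grade column.

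**The adverse event route.** Under Protocol 10.3.6.2, a laboratory deterioration is reported as an adverse event only if it meets the criteria for one and the investigator judges it clinically significant. For abnormalities associated with the challenge agent, the text gives as an example "decreased neutrophils) may be recorded as AEs (at the discretion of the PI/investigator". Tables 14.3.1.2 and 14.3.1.3 then count the reported events by arm, preferred term and, in the second, severity.

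**The concern.** Safety against placebo is a secondary objective, and Table 2-1 says RV299 has not been tested before in people infected with RSV. The same table notes that some subjects reach about double the exposure of others at a given dose. The worry is therefore a few affected individuals rather than a shift of a whole arm. The direct description of such a signal is the number of participants per arm who develop a low count after first dose.

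The plan supplies that number only for lows that pass a clinical judgement. The judgement is made under blinding, but it still filters. The challenge virus is an accepted explanation for a neutrophil fall, so a drug effect could be attributed to infection and not recorded. Placebo participants receive the same virus, so a count of measured values in both arms avoids having to attribute each fall.

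**Working it through.** The plan states no figure to reproduce. The check is whether Table 14.3.2 can determine the number of participants with a new low.

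**Inputs.** 40 participants per arm (SAP 6.1). Statistics as fixed in the Table 14.3.2 shell. Laboratory baseline before first IMP (SAP 10.9.2, which overrides the general pre-inoculation baseline of SAP 10.1.1). The documents give no reference limits, so a lower platelet limit of 150 ×10⁹/L is assumed. The values are constructed for illustration.

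**Observed post-dose platelets (×10⁹/L).**

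- Arm A: 120, 167, 167, 167, 170, 171, 172, 178, 186, 195, 195, 204, 206, 210, 214, 216, 219, 222, 232, 235, 235, 243, 243, 244, 246, 248, 259, 263, 268, 275, 275, 283, 293, 293, 296, 303, 310, 327, 340, 350
- Arm B: 120, 127, 133, 133, 177, 181, 184, 189, 194, 195, 195, 210, 230, 231, 231, 232, 232, 233, 234, 235, 235, 240, 247, 254, 257, 257, 262, 272, 275, 275, 275, 275, 278, 280, 287, 287, 291, 314, 333, 350

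**Observed row.** Both arms have sum 9440 and sum of squares 2,341,564.

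- Mean = 9440/40 = 236.0
- SD = √[(2,341,564 − 40 × 236²)/39] = √(113,724/39) = √2916 = 54.00
- %CV = 100 × 54/236 = 22.88
- Order statistics 10/11, 20/21 and 30/31 give Q1 195, median 235, Q3 275
- Minimum 120, maximum 350

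**Baseline and change rows.** Let every participant have fallen by exactly 40, so that baseline = observed + 40. Both arms then have baseline mean 276.0, SD 54.00, median 275, quartiles 235 and 315, and range 160 to 390. The change row is −40 throughout with SD 0. All three rows agree between the arms.

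**New lows.** A new low is an observed value below the limit with a baseline at or above it. With a limit of 150, every baseline (at least 160) is in range. Arm A has 1 new low (120) and Arm B has 4 (120, 127, 133, 133).

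**Sensitivity to the limit.** The 1 and 4 hold for limits from 134 to 160. At 133 they become 1 and 2, and at 161 they become 0 and 3. At 168 the order reverses, to 3 and 2.

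**What the count would show.** Wilson interval: [p + z²/2n ± z√(p(1−p)/n + z²/4n²)]/(1 + z²/n), with n = 40 and z = 1.96.

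| New lows | % | Wilson 95% CI |
|---|---|---|
| 1/40 | 2.5 | 0.4 to 12.9 |
| 4/40 | 10.0 | 4.0 to 23.1 |

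Fisher exact, two-sided, 1/40 against 4/40: 2 × [C(40,1)C(40,4) + C(40,5)]/C(80,5) = 2 × (3,655,600 + 658,008)/24,040,016 = 0.36. Even 0/40 against 4/40 gives 2 × C(40,4)/C(80,4) = 2 × 91,390/1,581,580 = 0.12.

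**Across visits.** The visit rows cannot be combined into a count of participants low at any time after first dose, because the minima on two days may come from one participant or from two.

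**The case against.** The strongest reply is that this is a reporting preference. Protocol 9.4.7 promises laboratory evaluations presented descriptively by arm, and the SAP delivers that. No text promises a shift table. With about 80 participants, the requested number can be read from a listing that already shows treatment group, value, change, limits and flag. The planned minimum would also reveal that an extreme fall occurred. All of this stands, and it keeps the point minor.

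The context is also more reassuring than the dog findings alone suggest. Table 2-1 says the effects followed 14 days of dosing well above the human dose, that exposure at 65 mg is 2- to 4-fold below the no-effect level, and that five days of twice-daily dosing showed no myelosuppression through three weeks of follow-up. Those human data were still blinded and pooled with placebo (Protocol 2.2.1), but they bear on importance.

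The example is built to make its point. A uniform fall of 40 is a limiting case and the result depends on the limit. It shows what the table cannot exclude, not what is likely.

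A reader might infer that no planned table counts low blood counts by arm at all. The documents do not support that: Tables 14.3.1.2 and 14.3.1.3 count participants with low counts reported as adverse events, and the protocol uses CTCAE as the reference for their severity. What is missing is a count based on measured values.

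**Conclusion.** The point holds as a minor weakness in reporting. The planned tables show low blood counts per arm only where the investigator reported an adverse event. They do not give the number per arm with any new measured low after first dose, and Table 14.3.2 cannot be made to yield it: identical rows are compatible with 1 and 4 new lows among 40. That illustration rests on an assumed platelet limit (134 to 160 gives the same result) and on an assumed uniform fall.

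A reader might go further and infer that participants are inadequately monitored for myelosuppression, or that a safety estimate is wrong. Neither follows. Protocol 7.2 and 7.5 provide for discontinuation and safety review during the study, and Protocol 10.2 requires the investigator to document review of each laboratory safety report. None of these depends on the tables. The planned summaries are correct for what they describe, and the missing number can be recovered by hand from the listings. Nor would the count support a formal comparison with 40 per arm; its use is descriptive.

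**What to change.** Before unblinding, add one descriptive by-arm table to SAP 10.9.2 and 13.2, covering platelets, neutrophils, white cells, lymphocytes, reticulocytes and haemoglobin. For each, give n (%) of participants with any value after first dose below the lower reference limit, among those not below it at the pre-IMP baseline of SAP 10.9.2. Attach the Wilson interval that Protocol 9.4.2.1 already names for proportions. No test is needed. Specifying the rule now avoids choosing thresholds after the results are known.

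A cross-tabulation of baseline grade against worst post-dose CTCAE grade, where CTCAE grades the parameter, is optional.

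The cost is one extra table and no extra samples. The count uses values, limits and flags already in the haematology listing. The optional grading needs extra programming because the listing holds no grades.
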